5.3.10. Distribution of Emergency contact card

Volunteers will be provided with an emergency 24-hour telephone number to contact the on call study physician if needed. In an emergency situation this card will be used to inform the attending physician that the subject is in a clinical study and that relevant information can be obtained by contacting the study investigator. Volunteers will be instructed to keep this card on their person at all times for the duration of their participation in the study.

5.3.11. Clinical Reviews

All clinical reviews and procedures will be undertaken by a member of the study team. The procedures to be included in each visit are documented in Tables 2 and 3. Each review is assigned a time point and a window period within which the review will be conducted.

5.4 Screening Visit

5.4.1. Informed Consent

It is the responsibility of the Principal Investigator or co-investigator (where the responsibility has been delegated by the Principal Investigator as captured on the Site Signature and Delegation Log) to obtain written informed consent for each volunteer before performing any trial related procedure.

The study information sheet will be made available to the volunteer at least 24 hours prior to the screening visit.

At the screening visit, the volunteer will be fully informed of all aspects of the trial, the potential risks and their obligations. The following will be emphasised:

- Participation in the study is entirely voluntary
- Refusal to participate involves no penalty or loss of medical benefits
- The volunteer may withdraw from the study at any time.
- The volunteer is free to ask questions at any time to allow him or her to understand the purpose of the study and the procedures involved
- Other than potential immunity against SARS-CoV-2, there is no direct benefit from participation
- The volunteer's GP will be contacted to corroborate their medical history and confirm that the volunteer is eligible to take part in the study. Volunteers will only be enrolled in the study if written or verbal information regarding the volunteer's medical history is obtained from the GP
- The volunteer will be registered on the TOPS database (The Over-volunteering Prevention System; www.tops.org.uk)
- The aims of the study and all tests to be carried out will be explained. The volunteer will be given the opportunity to ask about details of the trial, and will then have time to consider whether or not to participate
- Blood tests can include some genetic tests (participation in this study will not be affected by the decision to allow or not allow genetic tests to be carried out)
- The risks of participating in the study will be fully explained
- Study samples and data might be shared with other institutions within the UK and Europe, investigating the immune response to SARS-CoV-2. These will be anonymised.
- Study samples and data will be stored indefinitely either as part of an ongoing ethically approved study or in a human tissue authority (HTA) licensed biobank.
- Volunteers will be given the option to be contacted in the future for possible follow up trials looking at COVID-19

The aims of the study and all tests to be carried out will be explained. The volunteer will be given the opportunity to ask any questions that they have and will then have time to consider whether or not to participate. If they do decide to participate, they will sign and date the consent form and will be given a copy to keep. The original consent form will be stored as source documentation. These forms will also be signed and dated by the Investigator.

Details of the informed consent discussion will be recorded in the volunteer's medical record. This will include the date consent was given, with the name of the trial and the version number of the Participant Information Sheet and Informed Consent Form. Throughout the trial the volunteer should have the opportunity to ask questions about the trial and any new information that may be relevant to the volunteer's continued participation should be shared with them in a timely manner. On occasion it may be necessary to re-consent the volunteer, for example if new information becomes available or an amendment is made to the protocol that might affect the volunteer's participation in the trial. In this case the process above will be followed and the volunteer's right to withdraw from the trial respected.

5.4.2. Screening Clinical Assessments

No trial specific procedure should be carried out prior to signing the consent form for this study. All potential volunteers will have a screening visit, which may take place up to 90 days prior to vaccination. Informed consent will be taken before screening, as described in **section 5.4.1**. If consent is obtained, the procedures indicated in the schedule of events will be undertaken including a medical history, physical examination, blood tests, and urine test. To avoid unnecessary additional venepuncture, if the appropriate blood test results for screening are available for the same volunteer from a screening visit for another study, these results may be used for assessing eligibility (provided the results date is within the 3 months preceding administration of the first dose of pEVAC-PS).

Abnormal clinical findings from the medical history, physical examination and all tests at screening will be assessed by a clinician referring to site-specific laboratory adverse event grading tables which are filed in the trial master file (TMF). Any abnormal test result deemed clinically significant may be repeated to ensure it is not a single occurrence. If an abnormal finding is deemed to be clinically significant, the volunteer will be informed and appropriate medical care arranged with the permission of the volunteer.

The eligibility of the volunteer will be reviewed by the study clinician at the end of the screening visit and again when all results from the screening visit have been considered and a copy of the volunteer's medical history has been received from the GP. Decisions to exclude the volunteer from enrolling in the trial or to withdraw a volunteer from the trial will be at the discretion of the Investigator. If eligible, a day 0 visit will be scheduled for the volunteer to receive the vaccine.

5.4.3. Study Identifier Code (SIC) Allocation

Volunteers will be allocated a 3-digit subject identifier code (SIC). This will be allocated by the site reflecting the order of consent to the study within the site. For example, the third subject who signed an informed consent form at the study site will be identified as Subject 003. All study documents (e.g. CRFs, clinical documentation, sample containers, drug accountability logs, etc.) will be identified with the SIC.

The site study team will add the patient's allocated SIC to the site screening & recruitment log and keep it in the Investigator Site File.

5.4.4. Request of Medical History from GP

The volunteer's GP will be contacted to corroborate their medical history. Volunteers will only be enrolled in the study if written or verbal information regarding the volunteer's medical history is obtained from the GP. In cases where verbal consent is given, the study investigator conducting the telephone call will document the discussion and this will be filed in the volunteer's medical notes.

5.4.5. The Over-Volunteering Prevention System (TOPS)

Volunteers will be excluded from the study if they are concurrently involved in another trial. In order to check this, volunteers will be asked to provide their National Insurance or Passport number (if they are not entitled to a NI number) and will be registered on a national database of participants in clinical trials (www.tops.org.uk).

5.5 Participant visits

5.5.1 Vaccination Visits

Following review of safety blood results and GP medical history, eligible subjects will be booked to attend a vaccination visit on Day 0. After re-checking inclusion and exclusion criteria, an abbreviated physical examination (at the investigator's discretion) and measurement of physical observations, subjects will be enrolled into a study group for vaccination. Volunteers will be enrolled into each group or subgroup sequentially. Volunteers will be informed of which group they will be enrolled into. Volunteers will not be randomised into a group in this study.

If medical status and/or physical examination suggest significant changes have occurred since screening, the Day 0 visit can be re-scheduled, or the subject excluded from the study if he/she fails to meet the inclusion and exclusion criteria. The study team will advise the volunteer prior to the dosing visit that receipt of licensed vaccines e.g. (FLU vaccine) is not permitted within the month preceding vaccination or the month following each vaccination. Should a volunteer have received a licensed vaccine in the month prior to pEVAC-PS vaccination the Day 0 visit will be rescheduled to an acceptable time-point.

Before vaccination, the investigator must check for any symptoms of an acute illness or body temperature \geq 37.5°C. In such a situation, the subject may be vaccinated at a later date within the screening window or be withdrawn at the discretion of the investigator. The vaccine will be administered as detailed in **Section 6.3** *Dosage and administration of study vaccine'*.

Following vaccine administration, subjects will be observed for a minimum of 60 minutes for the development of any acute reactions, or longer if deemed necessary.

Subjects will be provided with a subject diary, thermometer, and ruler to measure and record body temperature, solicited local and systemic AEs.

This will be repeated on Day 28 for administration of the second dose of vaccine.

If the volunteer has remained well during this observation period, they may go home and will receive a follow up telephone call the next day.

Any significant safety concerns that have arisen during the observation period will be communicated to the CI and local safety monitor. An extended period of observation will be instigated if necessary. In this unlikely event, the following procedures will be followed as a minimum:

- The volunteer will be accompanied in the observation area by a trial nurse or study investigator. The frequency of physical observations (blood pressure, pulse, temperature) will be determined by the CI, for example hourly (+/- 15 minutes).
- The trial clinician may initiate basic treatments for vaccine related symptoms including anti-pyretic and anti-emetic medication.
- Intravenous fluid can also be given for tachycardia or hypotension of grade 2 or above or for any other reason of clinical significance according to the trial investigators judgement.

If at any point following vaccination, the CI or local safety monitor identifies any acute clinical concern requiring urgent medical intervention, an acute admission for further clinical management will be arranged.

5.5.2 Subsequent Visits

Volunteers will return to the study site for follow up visits as specified in Table 2 and Table 3. Diary cards will be reviewed for details of solicited and unsolicited AEs for 28 days after each vaccination, and any new or undocumented medical issues or symptoms that have arisen will be assessed. Physical observations and venepuncture for immunology and safety bloods will be undertaken as per the applicable schedule of events. Information on medications administered will be recorded. On Day 1 volunteers that have been enrolled in Group 1 will be contacted via telephone to collect safety information (solicited and unsolicited AEs, SAEs and concomitant medications).

5.5.3 Participants under quarantine

Given the evolving epidemiological situation both globally and in the UK, should a participant be under quarantine and unable to attend any of the scheduled visits, a telephone/video consultation will be arranged using smartphone or computer app if clinically appropriate in order to obtain core study data where possible.

Participants with confirmed SARS-CoV-2 infection (COVID-19 Pathway)

Participants will be counselled at enrolment that should they receive a positive SARS-CoV-2 test (e.g. an antigen detection or nucleic acid amplification test, for example, via test and trace or occupational health services) they should contact the trial team on receipt of the positive result. A study doctor will be available to direct the volunteer for routine medical care via standard NHS pathways should that be appropriate, depending on the volunteer's clinical condition.

This COVID-19 pathway will apply to participants tested via symptomatic and asymptomatic pathways.

Once the participant has conveyed their result to the study team, and the study team confirm an appropriate test has been used (verbal discussion with participant as to how testing was obtained, confirmatory documentation will not be sought), an appointment will be arranged to review the participant. At this visit blood samples for safety (FBC, Biochemistry, CRP and others if deemed clinically relevant) and immunology (PBMCs and serum for cellular and humoral immune responses) will be taken, along with a nasopharyngeal swab for storage and subsequent viral isolation. Vital signs and other clinical data will be recorded.

Participants will be eligible if they can attend the site for a COVID-19 visit within 7 days of a positive test.

5.6 Discontinuation/withdrawal of study volunteers

The following medical occurrences associated with vaccine immunisation constitute absolute contraindications to further administration of vaccine. If any of these events occur during the study, the subject must be withdrawn and followed until resolution of the event, as with any adverse event:

- Anaphylactic reaction following administration of vaccine
- Pregnancy

The following adverse events constitute contraindications to administration of vaccine at that point in time; if any one of these adverse events occurs at the time scheduled for vaccination, the subject may be vaccinated at a later date, or withdrawn at the discretion of the Investigator. The subject must be followed until resolution of the event as with any adverse event:

- Acute disease at the time of vaccination. (Acute disease is defined as the presence of a moderate or severe illness with or without fever). All vaccines can be administered to persons with a minor illness such as diarrhoea, mild upper respiratory infection with or without low-grade febrile illness, i.e. temperature of ≤37.5°C/99.5°F.
- Temperature of \geq 37.5°C (99.5°F) at the time of vaccination.

In accordance with the principles of the current revision of the Declaration of Helsinki and any other applicable regulations, a volunteer has the right to withdraw from the study at any time and for any reason, and is not obliged to give his or her reasons for doing so. The Investigator may withdraw the volunteer at any time in the interests of the volunteer's health and well-being. In addition, the volunteer may withdraw/be withdrawn for any of the following reasons:

- Administrative decision by the Investigator.
- Significant protocol deviation.
- Volunteer non-compliance with study requirements.
- An AE, which requires discontinuation of the study involvement or results in inability to continue to comply with study procedures.
- Pregnancy

The reason for withdrawal will be recorded in the eCRF. If withdrawal is due to an AE, appropriate follow-up visits or medical care will be arranged, with the agreement of the volunteer, until the AE has resolved, stabilised or a non-trial related causality has been assigned. Any volunteer who is withdrawn from the study may be replaced, if that is possible within the specified time frame. The Local Safety Monitor (LSM) may recommend withdrawal of volunteers. Any volunteer who fails to attend for two or more follow-up visits during the study, despite active attempts to contact volunteer by trial team, will be deemed to have withdrawn from the study. The study team will make reasonable attempts to contact volunteers that do not return for scheduled visits or follow-up.

If a volunteer withdraws from the study, blood samples collected before their withdrawal from the trial will be used/ stored unless the volunteer specifically requests otherwise.

In all cases of subject withdrawal, except for those of complete consent withdrawal, long-term safety data collection including some procedures such as safety bloods, may continue as appropriate if subjects have received one or more vaccine doses and have indicated willingness to attend a relevant follow-up time point. Should a volunteer decide that they do not want to proceed with receiving a second dose of pEVAC-PS after receiving the first dose but agree to continue attending follow up visits they will be asked to attend at Day 1 (telephone call), Day 3, Day 7, Day 14, Day 28, Month 3 and Month 6.

5.6.1 Volunteer Replacement

The investigator and local safety committee will assess whether any volunteers that withdraw from the study after enrolment will need to be replaced. All existing safety and adverse event data from withdrawn participants will be provided to the local safety committee as part of the safety report.

5.7 Duration of Study

Volunteers will be considered to be enrolled in the study on receipt of their first vaccination. Volunteers will remain in the study for a maximum of 18 months (+/- 28 days) after being enrolled (this includes up to 6 months during the recruitment and dosing phase with a follow-up period of up to 12 months).

The study is considered to be complete upon last volunteer/last visit at the site. The end of study is defined as the completion of the testing of samples, to be achieved no later than 12 months after the date of the last visit of the last volunteer.

5.8 Sample handling

5.8.1. Laboratory work

This immunogenicity study will be conducted in laboratories at the Lab of Viral Zoonotics, at the University of Cambridge. The laboratories that will be used are 207 and the equipment bay, with the North laboratory as a back-up facility. The ELISA will be carried out in 207.

5.8.2. Labelling of samples

As the clinical trial is open label, the serology lab (LVZ) at the University of Cambridge will be able to identify which samples are from which treatment group. Each blood sample will be labelled with subject number (e.g. 001), study protocol number (RHM MED 1776), study day (e.g. S, Day 0, 7, 14) and the date the sample was taken. The secondary container in which samples are shipped to LVZ will state the required storage conditions and will specify the nature of the samples (i.e. heparinised blood / SST blood). If any additional information which may breach patient confidentiality is present on sample tubes, LVZ staff will operate in accordance with the relevant SOP in dealing with such samples.

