3.1.1. Immunogenicity endpoints

The adaptive protocol is based on reviews of immunogenicity data which will be made 4 weeks following the second administration of pEVAC-PS (8 weeks following the first dose). The decision for how to proceed will be made on the basis of the proportion of participants within each group who have seroconverted. Seroconversion will be defined as a positive readout from the SARS-CoV and/or SARS-CoV-2 RBD ELISA. The dose used for each group will be classified as either having met immunogenicity target, failed to meet immunogenicity target, or had very poor / no response. Proportions of participant seroconversion will be classed as the following:

Stage 1 – Meets immunogenicity target if 5 or 6 out of 6 participants have at least a 2-fold increase in Ab titre (at 0.2mg) we proceed to Expanded Group 1.

- Stage 2 (Expanded Group 1) if 12/12 participants have a 2-fold increase in Ab titre (at 0.2mg) consider to re-formulate and reduce the dose for a new study.
- Stage 2 (Expanded Group 1) if 10 or more of the 12 participants have at least a 2-fold increase in Ab titre (at 0.2mg) we select 0.2mg as the optimum dose to move forward into a Phase II study.
- Stage 2 (Expanded Group 1) if <=9 participants have a 2-fold increase in Ab titre (at 0.2mg) then a further 9 participants will be recruited to group 2a (0.4) and 2b (0.8mg) each, to be run in parallel.

 - The study will conclude after running groups 2a and 2b.

Stage 1 – Fails to meet immunogenicity target if only 3 or 4 out of 6 participants have at least a 2-fold increase in Ab titre, then we proceed to Groups 2a (0.4mg) and 2b (0.8mg) in parallel.

- Stage 2 if 7-9 or more participants have a 2-fold increase in Ab titre (at 0.4 or 0.8 mg) we expand whichever group has the higher number of responders. If both groups 2a and 2b have 9 responders, we will expand the lower dose.
- Stage 2 if <7 participants have a 2-fold increase in Ab titre (at 0.4 or 0.8 mg) we move to Stage 3 and increase dose to 1.2mg.

Stage 1 – With a poor response, if 2 or less participants out of 6 have a 2-fold increase in Ab titre, we proceed to Groups 2a (0.8mg) and 2b (1.2mg) in parallel.

- Stage 2 if 7-9 participants have a 2-fold increase in Ab titre (at 0.8 or 1.2mg) we expand whichever group has the higher number of responders.
- Stage 2 if <7 participants have a 2-fold increase in Ab titre at 0.8mg and 1.2mg the trial will conclude.

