5.8.3. Storage of samples

Blood samples will be processed into serum and PBMCs on the day of receipt at LVZ in accordance with local SOP or separated at the study site and shipped frozen to LVZ in batch. Processing of blood into serum and PBMCs will be carried out in line with local risk assessment.

Serum and PBMC samples will be aliquoted into cryotubes labelled by LVZ after preparation from blood. Labels will contain identical information to the blood tubes, but will also specify 'human serum' or 'human PBMCs' to denote the type of sample contained within the vial. Serum and PBMC vials will be numbered sequentially for each patient (e.g. S01, P01, P02) in accordance with local SOP. LVZ will only identify samples from these labels.

Once serum and PBMCs have been prepared, samples will be stored in cryoboxes below - 60°C in accordance with SOP MIG/001. PBMCs may be transferred to liquid nitrogen for long-term storage. Serum samples will be removed from the ultra-low temperature (ULT) freezer as and when they are tested and will be returned to the ULT freezer after testing.

The samples will be kept until the clinical study report has been finalised. The sponsor will inform LVZ when the clinical study report has been finalised and whether samples are to be returned to the study site or are to be destroyed at LVZ. If the sponsor does not inform the LVZ what to do with the samples then LVZ will return any remaining aliquots to the study site after the clinical study report has been finalised.

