5.8.4. Shipment of samples

Samples will be shipped to LVZ by courier at ambient temperature on the day of blood being drawn, within normal working hours or separated and frozen at the study site to be shipped in batch at a later date. A schedule of sampling dates will be prepared by the study site and agreed with LVZ in advance to ensure availability of staff for sample receipt and processing. Any changes to this sampling schedule will be communicated to and agreed with LVZ in advance.

Upon receipt, the blood samples will be taken to test facility laboratories where details on the sample tubes will be checked to ensure that samples received are as expected. Any discrepancies will be recorded on the blood sample shipment form. The original forms will be filed in the RHM MED1776 study test sample file. For each shipment, PDF copies of the completed forms will be e-mailed to the Chief Investigator at the study site to document receipt. This e-mail will also state the sample numbers and volumes received, the date of receipt and the nature of any discrepancies. This e-mail will also request documented approval to proceed

with testing of this batch of blood samples, once processed into serum/PBMCs. A batch of samples will only be tested at LVZ once written approval is received from the sponsor for that batch.

6. Investigational Product

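### The laboratory running the RBD ELISA can see group and study day, although responder counts from that assay steer the stage-to-stage dose branches and one call can change a branch

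*Protocol*

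**What the plan says.** **Labels.** Section 5.8.2 gives the open-label design as the reason why "the serology lab (LVZ) at the University of Cambridge will be able to identify which samples are from which treatment group". Each blood tube carries the subject number, the protocol number, "study day (e.g. S, Day 0, 7, 14) and the date the sample was taken". Section 5.8.3 carries this over to the vials that are assayed: "Labels will contain identical information to the blood tubes". It adds that the laboratory identifies samples from these labels only. Dose is not printed, but subject numbers follow the order of consent (section 5.4.3) and groups are filled in sequence (section 5.5.1).

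**Use of the assay.** Section 3.1.1 states: "The decision for how to proceed will be made on the basis of the proportion of participants within each group who have seroconverted". It names the assay ("Seroconversion will be defined as a positive readout from the SARS-CoV and/or SARS-CoV-2 RBD ELISA") and then sets the branches by counts of participants with a 2-fold titre rise: 5–6, 3–4 or at most 2 of 6 in Stage 1; 7–9 or fewer than 7 of 9 in Groups 2a and 2b; 10 or more, or 9 or fewer, of 12 in Expanded Group 1.

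**Handling.** Section 5.8.4 lets blood go to the laboratory on the day, or be "separated and frozen at the study site to be shipped in batch at a later date". Testing is released by shipment: "A batch of samples will only be tested at LVZ once written approval is received from the sponsor for that batch". Section 5.8.3 says: "Serum samples will be removed from the ultra-low temperature (ULT) freezer as and when they are tested".

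**Other inputs.** Section 8.1 adds tolerability to the dose-adaptation decision. It promises full source verification of safety data beforehand, but not of all immunogenicity data. Under section 3.1, the move from Group 2a to Group 2b depends on a 72-hour safety review.

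**The concern.** The stated reason does not lead to the stated rule. Participants and clinic staff know the dose in an open-label trial, but the person handling an ELISA plate need not know which serum is baseline, which is post-dose, or which dose was given.

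The responder call is a within-person ratio cut at 2, summed over 6, 9 or 12 people. Someone who knows that a borderline serum is a Day 56 sample could, without intending it, treat repeats, plate acceptance or curve handling differently from a Day 0 serum. When 2a and 2b are compared, knowledge of dose adds a second route, because section 3.1.1 expands the group with more responders. No control group exists in which such an effect would show. At stake is which dose branch the trial takes after Stages 1 and 2.

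**Working it through.** The protocol states no power, alpha or assay precision, so it has no figure of its own to reproduce. The check has three parts.

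**1. What the laboratory knows, by stage**

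| Decision | Study day visible | Dose visible | Does dose knowledge bear on the decision? |
|---|---|---|---|
| Stage 1 (6) | yes | yes | No: one dose only, so the exposure is study day |
| Expanded Group 1 (12) | yes | yes | No: one dose only |
| 2a v 2b (9 each) | yes | yes | Yes: the two counts are compared |

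**2. How often one call matters**

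Take the Stage 1 count as binomial with n = 6 and true responder rate p (assumed). One extra responder changes the branch when the count is 2 or 4. One fewer changes it when the count is 3 or 5. The formula is P(X = k) = C(6,k) p^k (1−p)^(6−k).

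| p | P(2) | P(4) | Sum: one up matters | P(3) | P(5) | Sum: one down matters |
|---|---|---|---|---|---|---|
| 0.5 | 0.234 | 0.234 | 0.47 | 0.313 | 0.094 | 0.41 |
| 0.6 | 0.138 | 0.311 | 0.45 | 0.276 | 0.187 | 0.46 |
| 0.7 | 0.060 | 0.324 | 0.38 | 0.185 | 0.303 | 0.49 |
| 0.8 | 0.015 | 0.246 | 0.26 | 0.082 | 0.393 | 0.48 |

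For a Stage 2 group of 9, one extra responder lifts the group to the cut of 7 when the count is 6. P(6) = 84 p^6 (1−p)^3 = 0.16, 0.25, 0.27 and 0.18 at the same four values of p.

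These figures are the chance of standing next to a cut. They are not the chance that a call is wrong, which depends on reader behaviour the document does not describe.

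**3. Run-to-run shift, conditional on separate runs**

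This part applies only if a participant's Day 0 and Day 56 sera are read in different runs, which the protocol neither states nor rules out. Assay precision is assumed. Take the log ratio as Normal with mean ln(true mean rise) + ln(shift) and variance s² + 2 ln(1+CV²), where s is the between-person SD of the log rise. The responder probability is P(ratio ≥ 2) for one antigen.

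- No true rise, s = 0, no shift: at CV 20%, the SD is √(2 ln 1.04) = 0.280, and P = 1 − Φ(0.693/0.280) = 0.7%. At CV 30%, 40% and 50% it is 4.7%, 10.2% and 15.0%.
- From individual to branch, CV 30%: the chance of at least 3 of 6 false responders is 0.2% with no shift and 16.0% with a 1.5-fold upward shift. At least 5 of 6 stays at 0.4% even with that shift. Across CV up to 50% and shift up to 1.5-fold, the chance of at least 5 of 6 is at most 1.8%.
- Borderline response (true mean rise 2-fold, s = 0.5, CV 20%):

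| Shift in Day 56 run | Responder probability | P(≥5/6) | P(≤2/6) |
|---|---|---|---|
| 0.8-fold | 0.349 | 0.022 | 0.650 |
| none | 0.500 | 0.109 | 0.344 |
| 1.25-fold | 0.651 | 0.322 | 0.116 |

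A shift shared by a run would therefore seldom create a false Stage 1 target in true non-responders on one antigen. It could move a borderline group across either cut.

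**The case against.** The strongest reply is that this is a disclosed choice in a small phase I trial. Immunogenicity is a secondary objective, no formal test is planned on the primary outcomes, and how the plate is read is not stated. If an instrument reads it under a fixed procedure, little room is left for judgement. That limits the likely size of the effect. It does not justify the rule, because repeats, plate acceptance and curve handling can still involve choices, and masking costs little.

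Three stronger readings are tempting, and the document does not support them.

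- *The ELISA decides every dose step.* It does not. The 2a-to-2b step is a safety gate (section 3.1), and tolerability enters the other decisions (section 8.1).
- *Batch-wise testing means that Day 0 and Day 56 are read in separate runs, so drift is built in.* The batch in section 5.8.4 is a shipment, not an assay run. Sera may be frozen and sent together, and run rules may sit in a laboratory SOP that is not shown. Drift is a possibility left open, not a demonstrated defect.
- *Knowing the group threatens every stage.* Stage 1 has a single dose, so there only knowledge of study day matters. Dose knowledge matters when 2a is set against 2b.

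It is also fair to say that the false-responder rates in part 3 do not measure reader bias, and that they are not what the fix would save, since same-run testing still leaves within-run error.

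**Conclusion.** The point holds for the labelling. Sections 5.8.2 and 5.8.3 leave the laboratory that produces the decision readout aware of study day and group, for a reason that does not require it. The counts are small and the cuts are sharp: for true responder rates of 0.5 to 0.8, Stage 1 has a 0.26 to 0.47 chance of ending where one extra call changes the branch. That range assumes independent participants with a common responder rate. The reader effect itself has no computable size, and nothing in the document shows that one would occur.

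The same-run question is secondary. The drift figures rest entirely on assumed assay precision, an assumed shift and separate runs. They show only why it is worth closing a gap the text leaves open. The change is worthwhile before Stage 1 sera are tested; the flaw does not invalidate the design.

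**What to change.** **Sections 5.8.2 and 5.8.3.** For sera used in the stage decisions, use the route of separation and freezing at the site that sections 5.8.3 and 5.8.4 already permit. Label these vials with a random code that shows neither subject number, study day, date nor group. The site holds the key until the ELISA results for that stage are locked. Make one exception: the RBD result needed for the exclusion criterion in section 4.2 has to be linked to the volunteer before enrolment.

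**Section 5.8.4, as a secondary safeguard.** The site supplies a coded plate map so that each participant's Day 0 and Day 56 sera are assayed in the same run without revealing which is which. State that the Day 0 value from that run is the baseline for the 2-fold call, so that an earlier reading does not create a second baseline.

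**Cost.** Recoding work at the site, a site-held key and plate map, and one repeat Day 0 assay where that serum was read earlier. Sera are already aliquoted and stored below -60°C. Same-day shipment of whole blood would not serve for these decision sera, because on that route the laboratory itself labels the vials.
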